3.2.1.4 Choice of study population

The study population was selected to balance demands on representation of the future patient population and limit bias caused by confounding factors. The prevalence of type 2 diabetes increases with age and since there is no upper age limit the study will include also elderly patients. Women are not allowed to be or to become pregnant since saxagliptin has not been tested in pregnant women and the risk to the embryo, foetus, or infant are unknown.

In order to ensure that the study population is representative of the future target population, the limit for HbA1c is set to >6.5 to $\le 10\%$ (value from the enrolment visit). The HbA1c criterion was selected to permit patients with a wide range of glycaemic control, thereby helping to broaden the potential applicability of the study. The lower bound in this interval (ie, >6.5%) reflects continually evolving treatment guidelines such as the International Diabetes Federation Global Guideline for type 2 diabetes 2005 (International Diabetes Federation 2005), The National Institute for Clinical Excellence Guideline Management of type 2 diabetes – Management of Blood Glucose (National Institute for Clinical Excellence 2002), American Diabetes Association Position Statement on Standard of Medical Care in Diabetes 2006 (American Diabetes Association 2006), and the American Association of Clinical Endocrinologist Medical guidelines for the management of diabetes mellitus (American Association of Clinical Endocrinologists 2002). Although individual guidelines recommend treatment to normal HbA1c levels, the risk of hypoglycaemia may limit the possibility to achieve this in clinical practice. Treatment with a compound with the mode of action as saxagliptin with low risk of hypoglycaemia may, however, offer the possibility to normalise blood glucose and achieve an optimal glycaemic control. The upper bound of this interval (ie, $\leq 10\%$) is a commonly used and accepted value employed in studies of patients with diabetes.

Measures are taken to ensure that not more than approximately 25% of the population has HbA1c <7 %. The HbA1c levels of the randomized patients will be monitored closely so that when the cohort is estimated to have reached the aimed number, further enrolment to the >6.5

Clinical Study Protocol Drug Substance Saxagliptin Study Code D1680C00001 Date

to <7 % cohort will be discontinued and the lower bound of HbA1c for enrolment will be set at HbA1c \ge 7% for the remainder of the study.

The limitation regarding patients with renal impairment is based on restrictions for treatment with metformin.

The purpose of the remaining inclusion and exclusion criteria is to limit confounding factors that would complicate the interpretation of the results (eg, corticosteroid-induced type 2 diabetes, haemoglobinopathies that would interfere with the HbA1c analyses) or to exclude patients whose safety could be compromised by participation in the study.

3.2.2 Risk/benefit and ethical assessment

See the IB for an overall risk/benefit assessment of saxagliptin.

In a Phase II proof-of-concept study, all doses of saxagliptin were associated with a statistically significant and clinically relevant improvement in glycaemic control. Data from two phase III studies have also been evaluated. In summary, the safety and efficacy data collected to date from clinical studies in healthy volunteers and patients with type 2 diabetes indicate that the clinical safety and efficacy profile of saxagliptin support studies with 5 mg as the anchor dose. Studies on the long-term safety profile of saxagliptin are currently ongoing.

3.3 Selection of study population

3.3.1 Study selection record

Investigator(s) must keep a record of patients who were considered for enrolment but were never enrolled eg, a patient screening log. This information is necessary to establish that the patient population was selected without bias.

3.3.2 Inclusion criteria

For inclusion in the study patients must fulfil all of the following criteria:

Inclusion criteria at enrolment (Visit 1):

- 1. Provision of informed consent.
- 2. Diagnosed with type 2 diabetes.
- 3. Men or women who are ≥ 18 years of age at time of consenting upon Visit 1.
- 4. Women of childbearing potential (WOCBP) must be using an adequate method of contraception to avoid pregnancy throughout the study and for up to 4 weeks after the study in such manner that the risk of pregnancy is minimized.

WOCBP include any female who has experienced menarche and who has not undergone successful surgical sterilization (hysterectomy, bilateral tubal ligation or bilateral oophorectomy) or is not postmenopausal (defined as amenorrhea ≥ 12

Clinical Study Protocol Drug Substance Saxagliptin Study Code D1680C00001 Date

consecutive months; or women on hormone replacement therapy (HRT) with documented serum follicle stimulating hormone (FSH) level >35mIU/mL).

Even women who are using oral, implanted or injectable contraceptive hormones or mechanical products such as an intrauterine device or barrier methods (diaphragm, condoms, spermicides) to prevent pregnancy or practicing abstinence or where partner is sterile (eg, vasectomy), should be considered to be of child bearing potential.

WOCBP must have a negative urine pregnancy test (minimum sensitivity 25 IU/L or equivalent units of human chorionic gonadotropin (hCG)) within 72 hours prior to the start of study medication.

5. Treatment with metformin alone on stable doses of 1500 mg or higher per day for at least 8 weeks prior to Visit 1.

Inclusion criteria at lead-in (Visit 2, laboratory values from Visit 1):

6. HbA1c >6.5% and ≤10.0%. NB Enrolment of patients having HbA1c >6.5% to <7 % will be stopped when the cohort of randomised patients having HbA1c <7 % is approximately 25% and the lower bound of HbA1c for enrolment will be set at HbA1c ≥7% for the remainder of the study.

3.3.3 Exclusion criteria

Any of the following is regarded as a criterion for exclusion from the study:

Exclusion criteria at enrolment (Visit 1):

- 1. Type 1 diabetes, history of diabetic ketoacidosis or hyperosmolar non-ketonic coma.
- 2. Pregnant or breastfeeding patients.
- 3. Insulin therapy within one year of enrolment (with the exception of insulin therapy during a hospitalization or use in gestational diabetes).
- 4. Previous treatment with any DPP-4 inhibitor.
- 5. Treatment with thiazolidindione within 12 weeks prior to Visit 1.
- 6. Treatment with systemic glucocorticoids other than replacement therapy. Inhaled, local injected and topical use of glucocorticoids is allowed.
- 7. Treatment with cytochrome P450 3A4 (CYP450 3A4) inducers (carbamazepine, dexamethasone, phenobarbital, phenytoin, rifampin).

- 8. Treatment with human immunodeficiency virus (HIV) treatment/antiviral drugs (delavirdine, indinavir, nelfinavir, ritonavir, saquinavir).
- 9. Potential allergy to metformin, saxagliptin, glipizide, or placebo or formulation excipients.
- 10. Contraindications to therapy as outlined in the saxagliptin IB, metformin package insert, or glipizide package insert.
- 11. Congestive heart failure with functional deficit defined as New York Heart Association (NYHA) class III or IV (see Appendix C) and/or left ventricular ejection fraction of $\leq 40\%$.
- 12. Significant cardiovascular history within the past 6 months upon Visit 1 defined as: myocardial infarction, coronary angioplasty or bypass graft(s), valvular disease or repair, unstable angina pectoris, transient ischemic attack, or cerebrovascular accident.
- 13. History of haemoglobinopathies (sickle cell anaemia or thalassemias, sideroblatic anaemia).
- 14. History of alcohol abuse or illegal drug abuse within the past 12 months.
- 15. Involvement in the planning and conduct of the study (applies to both AstraZeneca and Bristol-Myers Squibb staff or staff at the study centre).
- 16. Previous enrolment or randomization of treatment in the present study.
- 17. Participation in a clinical study during the last 90 days prior to Visit 1.
- 18. Donation of blood, plasma or platelets within the past 3 months prior to Visit 1.
- 19. Any condition where, in the opinion of the investigator, participation in this study may pose a significant risk to the patient or could render the patient unable to successfully complete the study.
- 20. Suspected or confirmed poor protocol or medication compliance as judged by the investigator.

Exclusion criteria at lead-in (Visit 2, laboratory values from Visit 1):

- 21. Serum creatinine \geq 133 µmol/L (\geq 1.5 mg/dL) for men, \geq 124 µmol/L (\geq 1.4 mg/dL) for women.
- 22. Active liver disease and/or significant abnormal liver function defined as aspartate aminotransferase (AST) >2x upper limit of normal (ULN) and/or alanine aminotransferase (ALT) >2xULN and/or total bilirubin >34 μmol/L (2 mg/dL).

- 23. Creatine kinase (CK) $\geq 3xULN$.
- 24. History of positive serologic evidence of current infectious liver disease including hepatitis A viral antibody (anti-HAV), hepatitis B surface antigen (HBsAg), or hepatitis C virus antibody (anti-HCV). Patients who may have isolated positive antibody hepatitis B surface antigen (anti-HBs) can be included.
- 25. Any clinically significant abnormality identified on physical examination or laboratory tests, which in the judgement of the investigator would compromise the patients' safety or successful participation in the clinical study.

Exclusion criteria at randomization (Visit 3):

26. Any clinically significant abnormality identified on physical examination or ECG, which in the judgement of the investigator would compromise the patients safety or successful participation in the clinical study.

3.3.4 Restrictions

There are no restrictions on patients participating in this study with regards to diet, smoking, physical activity, etc, other than the inclusion and exclusion criteria listed above. The patients should not donate blood, plasma or platelets during the study.

Restricted concomitant medications are listed in Section 3.7; restrictions before performing an OGTT (applicable in a selection of countries (50 patients)) are detailed in Section 4.6.2, and fasting prior to laboratory assessments is detailed in Section 4.7.2.1.

3.3.5 Discontinuation of patients from treatment or assessment

3.3.5.1 Criteria for discontinuation

Patients may be discontinued from study treatment and assessments at any time. Specific reasons for discontinuing a patient from this study are:

- 1. Voluntary discontinuation by the patient who is at any time free to discontinue his/her participation in the study, without prejudice to further treatment.
- 2. Safety reasons as judged by the investigator, AstraZeneca and/or Bristol-Myers Squibb Pharmacovigilance.
- 3. Severe non-compliance to protocol as judged by the investigator and/or AstraZeneca.
- 4. Incorrect enrolment or randomization, ie, the patient does not meet the required inclusion/exclusion criteria for the study.
- 5. Patient lost to follow-up (as defined by, unable to reach the patient after 3 documented phone calls, fax, e-mail, or attempts to contact him/her through patient

locator agencies (if allowed per national regulation) and having sent one letter by registered/certified mail; all should be documented in the patients medical records).

Study specific discontinuation criteria are listed below. The FPG and HbA1c values will be measured at the central laboratory.

- 6. Use of (need for) any antihyperglycaemic medication other than investigational product or open-label metformin for more than 14 consecutive days, however insulin during hospitalisation is allowed.
- 7. Treatment with chronic systemic glucocorticoids. However, two temporary periods no longer than 7 days each are allowed.
- 8. Severe and/or frequent hypoglycaemic events, defined as ≥ 1 major event or recurring minor events and the possibility of down-titration and contributing factors (eg, excessive physical activity) has been evaluated.
- 9. Patients whose double blind treatment codes are broken by the investigator.
- 10. Pregnancy.
- 11. FPG >15.0 mmol/L (>270 mg/dL) at Visit 4 (Week 3) confirmed at a repeated measurement.
- 12. FPG >13.3 mmol/L (>240 mg/dL) at Visit 7 (Week 12) and on maximum titrated tolerated dose for at least two weeks confirmed at a repeated measurement.
- 13. FPG >12.2 mmol/L (>220 mg/dL) at Visit 9 (Week 18) and on maximum titrated tolerated dose for at least two weeks confirmed at a repeated measurement.
- 14. FPG >11.1 mmol/L (>200 mg/dL) at Visit 10 (Week 24) confirmed at a repeated measurement.
- 15. HbA1c >8.0% at Visit 11 (Week 30) and Visit 12 (Week 39).
- 16. HbA1c >7.5% at Visit 13 (Week 52), Visit 14 (Week 65) and Visit 15 (Week 78).
- 17. HbA1c >7.0% at Visit 16 (Week 91).
- 18. Absolute lymphocyte count \leq 400 cells/ μ L confirmed at a repeated measurement, see Appendix D.
- 19. Thrombocyte count <75 000 cells/μL confirmed at a repeated measurement, see Appendix E.

20. Increase in serum creatinine to a level of \geq 133 μ mol /L (\geq 1.5 mg/dL) for men, \geq 124 μ mol/L (\geq 1.4 mg/dL) for women confirmed at a repeated measurement, see Section 3.3.5.2.

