3.3.5.4 Criteria for entering the action plans

If any of the following criteria is fulfilled, the patients must enter the action plan, Appendix D or E, respectively.

Absolute lymphocyte count \leq 500 cells/ μ L, see Appendix D.

Thrombocyte count <75 000 cells/µL, see Appendix E.

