1. ALGORITHM FOR THROMBOCYTOPENIA

1.1 Overview of procedures

[figure not shown]
1.1.1 Patients who experience a platelet count <75,000 cells/μL during the double-blind Period C and D:

The Investigator, the Sponsor and the AstraZeneca representative will be notified by the central laboratory when any patient experiences a platelet count <75,000 cells/ μ L. The investigational product should be held immediately and a repeated blood sample should be taken. In addition a blood sample for assessment of saxagliptin and BMS-510849 plasma concentration should be obtained, refer to Section 4.5.1 and 4.7.1.3 of the Clinical Study Protocol. If platelet count <75,000 cells/ μ L is confirmed, the central laboratory will review the peripheral blood smear and notify the Investigator, the Sponsor and the AstraZeneca representative as to whether the smear is compatible with the reported decrease in platelet count.

- If the peripheral blood smear **is not compatible with** the reported decrease in platelet count (eg, clumped platelets), complete blood count (CBC) with differential is to be repeated within 72 hours of notification of the decreased platelet count. The Investigator, the Sponsor and the AstraZeneca representative should be notified of the results.
- If the peripheral blood smear **is compatible with** the reported decreased platelet count, or if the peripheral blood smear **is not reviewed within 48 hours** of the notification of the decreased platelet count, within 72 hours two CBCs with differential will be drawn and sent to local and central laboratories, respectively (the local CBC result received will be used to navigate the next step in the thrombocytopenia algorithm). Also within 72 hours, the patient will undergo brief physical examination including vital signs, skin and mucous membrane examination, urinalysis, and assessment for fecal occult blood. A **plasma** sample for anti-platelet antibodies will be drawn and sent to the central laboratory.
- If the repeat platelet count is ≥75,000 cells/µL, the investigational product may be reinstated unless otherwise contraindicated. A follow-up CBC should be performed one week after restarting blinded investigational product.

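### Criterion 19 and Appendix E act on different platelet counts, so a patient with two counts below 75,000 and then a recovered count has two different outcomes in the protocol

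*Protocol*

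**What the plan says.** Section 3.3.5.1 of the protocol introduces its numbered list with "Specific reasons for discontinuing a patient from this study are". Item 19 is a thrombocyte count below 75 000 cells/µL "confirmed at a repeated measurement, see Appendix E".

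Section 3.3.5.4 deals with entry to the appendix. A count below 75 000 cells/µL, with no confirmation required, means that "the patients must enter the action plan, Appendix D or E, respectively".

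Appendix E, Section 1.1.1, then sets out these steps:

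- At the first low count: "The investigational product should be held immediately and a repeated blood sample should be taken".
- If the low count "is confirmed, the central laboratory will review the peripheral blood smear and notify the Investigator" and others of the result.
- If the smear does not fit the low count, a "complete blood count (CBC) with differential is to be repeated within 72 hours of notification of the decreased platelet count".
- If the smear fits, or is not reviewed within 48 hours, two blood counts are drawn within 72 hours, one for a local and one for the central laboratory. The local result steers the next step.
- If the repeat count is 75,000 or more, "the investigational product may be reinstated unless otherwise contraindicated", with a follow-up count one week after restart.
- If the repeat count is below 75,000, the patient is discontinued from investigational product.

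**The concern.** Criterion 19 and Appendix E share a threshold and their first two steps, an alert count and a confirming count. They part at the second count. Criterion 19 treats a confirmed low count as a reason to leave the study. Appendix E treats it as the start of a work-up that can end in restarting product. The criterion refers the reader to the appendix, but the appendix does not act at the point the criterion names.

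What is at stake is consistent handling of a haematological safety signal. The study runs at approximately 160 centres (Section 3.1). Two of them could see the same three counts, each follow the written protocol, and reach different decisions on whether the patient continues. A patient could also restart product after meeting a listed reason for discontinuation.

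**Working it through.** No sample size, power or error-rate figure bears on this point, so the check is a comparison of the two texts. Write L for a count below 75,000 cells/µL and H for a count of 75,000 or more, and follow each possible sequence.

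| Sequence | Criterion 19 (Section 3.3.5.1) | Appendix E, Section 1.1.1 | Comparison |
|---|---|---|---|
| L, H | Not met, since the low count is not confirmed | Confirmed-low branch not entered | No conflict |
| L, L, H | Met at count 2: reason to discontinue from the study | Count 2 leads to smear review and a further count; count 3 allows restart | Different outcome |
| L, L, L | Met at count 2 | Discontinued from investigational product at count 3 | Different timing; study versus product |

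An illustration of the second row is 70,000, then 72,000, then 80,000. Criterion 19 is met at 72,000. Appendix E permits restart at 80,000.

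The table depends on which count each text means.

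1. **Appendix E, second count.** The appendix orders a repeat sample after the alert count and describes a low result on it as confirmed. Criterion 19 uses the same word for its trigger.
2. **Appendix E, deciding count.** Each smear result (compatible, not compatible, not reviewed in time) leads to at least one further blood count. On the compatible or not-reviewed branch the text says that the later local count steers what follows, and the steps listed next are restart and discontinuation. The deciding count thus comes after confirmation.
3. **The lymphocyte rule as comparator.** Criterion 18, directly above criterion 19, has the same wording about a repeated measurement for counts of 400 cells/µL or less and points to Appendix D. Appendix D requires discontinuation from investigational product when the second sample confirms the low count. There the criterion and its appendix act at the same count. A site that reads criterion 19 in the same way would discontinue at count 2.
4. **Precedence.** Section 3.3.5.4 requires entry to the action plan but does not say that the plan overrides criterion 19. The reference to Appendix E in criterion 19 does not say so either.
5. **Object of discontinuation.** Criterion 19 stands in a list of reasons for leaving the study. Appendix E speaks of leaving investigational product. Appendix D, unlike Appendix E, also schedules an end-of-study visit, so the platelet texts leave this second difference open.

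**The case against.** The strongest reply is that these are not competing rules. Every patient with a single low count must enter Appendix E under Section 3.3.5.4, and criterion 19 itself points there, so the appendix is the operative text and the repeated measurement is whatever Appendix E finally decides on. Section 4.6.2.1 also refers to thrombocytopenia as handled by the action plans.

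Two features of Appendix E support a reading in which its repeat count is the second count, which would agree with criterion 19:

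- Within the discontinuation step, haematology referral is required if any two counts after the alert are low. If discontinuation always needs an alert, a confirmation and a third low count, every discontinued patient already meets that condition.
- The only restart instruction is the one for a repeat count of 75,000 or more. If it applies only after confirmation, a patient whose first repeat is normal has product on hold and no written rule for restarting.

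These are fair points, and they show that Appendix E is not fully clear in itself. They do not remove the problem. The order of the appendix (confirmation, smear, further count, decision) favours the later count, and no sentence says which text governs. The flowchart is not shown and may clarify intent, but the two written rules would still need to match.

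Three stronger readings are tempting, and the documents do not support them:

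- A reader might infer that the texts give flatly opposed mandatory orders. Both are partly permissive: Section 3.3.5.1 opens by saying that patients may be discontinued, and Appendix E allows restart rather than requiring it. A site could even treat a met criterion as a contraindication to restarting.
- A reader might infer that the patient's per protocol status is left undetermined. Section 6.3.3 bases it on completing the 52 weeks without a reason for exclusion, and leaves the explicit exclusions to the SAP. No gap can be claimed there.
- A reader might infer that patients stay on product while low counts are being checked. Appendix E holds product at the first low count and asks for a recovered count before any restart.

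**Conclusion.** The point stands as an internal inconsistency in a safety stopping rule. For two low counts followed by a recovered count, criterion 19 and Appendix E lead to different outcomes. For three low counts they differ in timing and in whether the patient leaves the study or only the product; because product is already on hold, the timing difference is in the decision and not in dosing.

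The effect is confined to patients with at least two counts below 75,000. The documents give no expected frequency; few such patients are likely, which is an assumption. No effect on sample size, power, type I error or per protocol status is claimed.

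The conclusion rests on reading the repeat count in Appendix E as the one taken after confirmation, which the order of its steps favours, and on the written text alone. It takes no position on which clinical rule is right. The correction is worth making because it is specific and cheap and concerns a safety decision.

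**What to change.** Reconcile criterion 19 in Section 3.3.5.1 with Appendix E, Section 1.1.1. Both should state:

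- which platelet count decides;
- what follows from it;
- whether discontinuation is from the study or from investigational product.

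The flowchart in Appendix E should be checked against the agreed wording. The sponsor's clinical team must choose the rule; none is proposed here.

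The cost is a short protocol amendment and a letter to sites. Under Section 7.4 an amendment must be notified to or approved by each Ethics Committee and, where applicable, the local regulatory authority, so the change could be combined with the next planned amendment, with the letter sent once it may be implemented. No change to sample size or to the statistical analysis is needed.
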